11. PUBLICATIONS -----27

12. REFERENCES -----28

13. SUPPLEMENTS/APPENDICES ----- 32

 I CONSENT FORM TEMPLATE ----- 32

 II LIST OF QUESTIONNAIRES ----- 40

 III AE COLLECTION FORM TEMPLATE ----- 41

 IV DSMP ----- 42

 V STUDY ROSTER -----111

 VI SCHEDULE OF EVALS & ASSESSMENTS ----- 114

 VII BIostatistician CV ----- 117

 VIII LABORATORY PROCEDURES & EVALUATIONS ----- 126

STUDY SCHEMA AND DESIGN

Design Schema for Objective 2 (Phase 2):

We intend to randomize 210 CBP patients into the study with the expectation that 140 will finish successfully. The entire duration of the study will be 12 weeks with an initial 3-week baseline period (visits 1-3), a 6-week treatment period (visits 3-5), and a final 3-week washout period (visits 5-6). During the baseline period eligible **participants will be predicted as placebo responders and non-responders** based upon baseline brain scan results and specific questionnaire answers (properties determined from the results of **Phase 1**) and then classified on that basis. Participants will then be randomized within each classification group (placebo responders and placebo non-responders) at a ratio of 3:3:1 such that 42.5% receive active medication (naproxen/omeprazole, 500/20mg, bid), 42.5% receive matching placebo treatment and 15% no treatment. Brain imaging, self-report questionnaire, and pain/mood rating measurement regimens are shown in **Figure 1**. Pain, mood, and pill ingestion will all be monitored by smart phone for the duration of the study, as well as determined in person at each visit.

[figure not shown]

Figure 1. Experimental schema for Phase 2. Expected changes in pain are shown in solid and dashed horizontal lines. We expect to see different pain outcomes for the various placebo and treatment combination groups. To be noted, we predict that the No Treatment group will have similar pain trajectory as those classified Non-responders and treated with placebo. As well, in the No Treatment group participants will be classified as placebo responders and placebo non-responders, but will not receive any treatment agent, therefore, their pain trajectory will be constant throughout the study.

STUDY SUMMARY

Title	BRAIN MECHANISMS FOR CLINICAL PLACEBO IN CHRONIC PAIN
Short Title	PLACEBO IN CHRONIC PAIN (PICP)
Protocol Number	Grant:
Phase	Grant Phase 2
Methodology	Double blind, randomized (see section 5.4 for more specifics on blinding)
Study Duration	12 weeks
Study Center(s)	Northwestern University

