2.0 STUDY OBJECTIVES

2.1 Primary and Secondary Objectives

- 2.1.1 To evaluate the interaction between placebo response and active treatment in individuals classified as placebo responders vs non-responders. Individuals in the No Treatment group will be used as a negative control to control for regression to the mean, duration of pain, and other potential confounds.

Hypothesis: Brain functional and anatomical properties between groups after 6 weeks of treatment will identify separate circuitry for placebo analgesia and active treatment analgesia; and these groups will show distinct time courses and magnitudes of analgesia.

- 2.1.2 To test and validate brain imaging and personality parameters identified in Phase 1 that predict the propensity for placebo response and use the results to classify participants into responders vs non-responders before study intervention.

Hypothesis: Brain- and behavioral- based parameters identified as markers of placebo response in the first phase of the study will accurately predict potential responders from non-responders at first scan. The classification before study intervention will closely correspond to the responses observed at the end of treatment period.

- 2.1.3 To identify gender dependence of placebo analgesia propensity and examine brain and personality gender differences that underlie the seeming higher propensity of females for placebo response.

Hypothesis: Sexual dimorphism of the human brain and behavioral/personality differences may have a potential interaction effect and predisposition on placebo propensity. We expect to identify gender-specific biomarkers that are sexually dimorphic with regard to placebo response.

- 2.1.4 Classification of placebo responders versus non-responders for 2.1.2 will be based on Equation 1 below:

$$p = (e^{f(x)}) / (e^{f(x)} + 1)$$

$$f(x) = -3.3586 + 1.6676 * \text{Maia_Emotion} - 0.2127 * \text{Erq_Suppress} + 34.8608 * \text{sign_permutation}$$

where a probability (p) <0.5 = predicts non-responder and a probability (p) ≥0.50 predicts responder.

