- Visit 2 (week -1): Baseline Scan (90 min). Approximately 14 days after visit 1, participants will return for their second visit. If a VAS score of > 5 mm on average over the course of the visit 1-visit 2 rating period is calculated and no changes in clinical status are reported or found, they complete a battery of questionnaires and undergo MRI procedures (anatomical and functional scans). Subjects will be queried about changes to health experienced since the last visit and asked if they exceeded 4 acetaminophen per day. In addition one of the pictures for visit 2, 4, and 5 will be conducted (see section 13.III). They will be asked to continue their phone/computer app ratings and return in approximately one week for visit 3. Participants will receive only rescue medication in sufficient quantities until the next visit. Additionally, participants will be randomized into a treatment versus no-treatment group at this time (information that the pharmacy will produce and keep).
- Interim between Visit 2 and Visit 3: Group classification Based on Predicted Response

In between visits 2 and 3, participant's scans will be analyzed by extracting the functional connectivity between frontal and sensorimotor networks (called "sign permutation" in Equation 1) and 2 questionnaire subscores will be calculated (MAIA emotion and ERQ suppression in Equation 1); all 3 parameters will then be entered into Equation 1. Based on the results of the model specified on page 10, participants will be classified as either placebo non-responders (probability < 0.5) or placebo responders (probability \geq 0.5).

After baseline scan, the subjects' MR images and data will be collected by research personnel and then will be given to a single member, the blinded assessor ([name]) who will have no interaction with the participants, therefore will remain blinded. The research personnel responsible for conducting the visit will download the MAIA and ERQ questionnaires from the REDCap database and calculate the scores for MAIA-Emotion and ERQ-suppression subscales to be used in the model.

(1) All MR images collected at the baseline scan will be uploaded to the server and pre-processed within 24 hours of the visit using our in-house pipeline.

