whether or not they took their medication. This will allow us to keep track of the stability and magnitude of pain and mood, as well as treatment compliance. To encourage them to keep up with this requirement, each time they submit these answers, they will receive 25 cents. Responses and payments will be logged automatically into a secure database that only study personnel will have access to; if participants miss more than 3 consecutive ratings in a row, research personnel will call or text them to remind them to rate or verify that their app is still working (they are automatically alerted via email by a program designed by the lab). The unblinded monitor designated for this study will check participants ratings bi-weekly to verify that ratings are being completed.

- Follow up: Patients will be asked if they wish to be added to our contact list to participate in future studies of the lab. They will also be asked if they accept to be contacted by phone 3 months and 6 months later to assess the long-term effects of the study intervention on their chronic pain intensity.

5.3 Randomization:

All randomization (and blinding, see next section) will be completed by NUCATS (see study roster in Location 2 for name of personnel). NUCATS will generate two randomization sequences, one for each group (predicted responders, Group A, and non-responders, Group B). This approach will ensure the proper 3:3:1 treatment allocation. We will use a variable block design (size of 5 and size of 10), throughout Phase 2 of the study to minimize temporal bias that can accompany longitudinal scanning studies. We don't anticipate much exclusion after randomization and enrollment based on our previous studies (although screen failures during the run-in are likely due to pain level or pathology lab results, for example). The Phase 2 overall sample size is 210 randomized 3:3:1, therefore n = 90 active treatment (n = 45 responders/non-responders), n = 90 placebo treatment (n = 45 responders/non-responders), and n = 30 no treatment (n = 15 responders/non-responders). We expect an attrition rate of ~33% for a final N = 140.

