8.0 STATISTICAL CONSIDERATIONS

8.1 Summaries of Design, Endpoints, and Analysis

8.1.1 Phase II: Study Design/Study Endpoints

Enroll and randomize 220 CBP patients into the study. Stratify into placebo responders and non-responders based on brain scan results at entry. We anticipate that about 50% of the patients will be placebo responders. All participants are randomized so that 40 receive placebo treatment, 40 active medication, and 20 no treatment. If Gender Supplement is awarded then randomization is slightly different: 60 receive placebo, 60 active medication, and 20 no treatment.

We assume that placebo responders and non-responders will show differential interaction with active medication treatment. We also expect to distinguish the four groups based on brain activity at the end of the trial, and show close correspondence between predicted and actual outcomes regarding placebo responses. Additionally, placebo non-responders should show a robust medication response, especially in comparison to the placebo non-responders receiving placebo treatment. Brain activity contrasts are done as a two-way (treatment groups) repeated measures (time: start vs. end) ANOVA (2RM-ANOVA). This is the procedure we implemented recently in a longitudinal neuroimaging study of pain chronification (Baliki et al., 2012). Post-hoc comparisons then reveal: 1) A contrast of brain activity at end of treatment between placebo non-responders with and without medication treatment to identify brain activity for bottom-up modulation of chronic pain. 2) Brain regions related to chronic pain are identified as areas commonly decreased with placebo treatment for placebo responders and medication treatment for placebo non-responders. 3) Top-down placebo and bottom-up medication effects are distinguished by identifying regions that distinctly increase in activity for placebo and medication treatments based on contrasts for the same groups. 4) The no treatment group brain activity is used as a higher-level contrast, which effectively corrects for this confound.

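### Brain contrast 3 compares placebo in predicted responders with drug in predicted non-responders, so treatment is confounded with a non-randomised class.

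*Combined protocol and SAP*

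**What the plan says.** Section 8.1.1 describes the imaging model: "Brain activity contrasts are done as a two-way (treatment groups) repeated measures (time: start vs. end) ANOVA". Four follow-up items are listed.

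- Item 1 compares predicted non-responders with and without medication at the end of treatment. This is a within-class comparison.
- Item 2 looks for "areas commonly decreased with placebo treatment for placebo responders and medication treatment for placebo non-responders".
- Item 3 separates top-down placebo effects from bottom-up medication effects by finding "regions that distinctly increase in activity for placebo and medication treatments based on contrasts for the same groups".
- Item 4 adds: "The no treatment group brain activity is used as a higher-level contrast, which effectively corrects for this confound".

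Class is a baseline prediction. Section 5.2.1 obtains it by "extracting the functional connectivity between frontal and sensorimotor networks" and combining that value with two questionnaire subscores in Equation 1 (section 2.1.4). The coefficient for the connectivity term is positive, so high connectivity pushes a participant towards the responder class.

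Treatment is randomised inside class. The Study Schema says: "Participants will then be randomized within each classification group (placebo responders and placebo non-responders) at a ratio of 3:3:1". Section 5.3 gives "n = 90 active treatment (n = 45 responders/non-responders), n = 90 placebo treatment (n = 45 responders/non-responders" and 15 per class with no treatment. Section 2.1.1 gives the untreated arm its role: "Individuals in the No Treatment group will be used as a negative control to control for regression to the mean".

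**The concern.** The only pair of groups named immediately before item 3 is the pair in item 2. Item 3 therefore compares one treatment in one class with the other treatment in the other class. Randomisation protects a comparison of arms within a class. It does not protect this one.

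The classes are also formed by a cut on the kind of measurement being tested. A group selected high on a noisy baseline tends to fall at the next scan, and a group selected low tends to rise. With no treatment effect at all, predicted non-responders on drug would tend to show increased frontal-sensorimotor connectivity relative to predicted responders on placebo.

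The hypothesis under objective 2.1.1 is that placebo and drug analgesia use separate circuitry, and section 2.1 goes on to claim a separation of top-down from bottom-up modulation. Item 3 is the listed contrast that would supply that conclusion.

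**Working it through.** **Inputs from the documents.** Section 5.3 plans 210 randomised 3:3:1 in two equal classes, with 140 completing. If dropout is even, completers per class are 140 × 3/7 ÷ 2 = 30 on drug, 30 on placebo, and 140 × 1/7 ÷ 2 = 10 untreated.

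**Assumptions (not in the documents).** Scan-rescan correlation r of 0.5, 0.7 or 0.85; correlation ρ of 0.4 or 0.7 between the classifying score and the baseline measure; class cut at the median of that score; two-sided alpha 0.05 per test, uncorrected.

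**The plan's own figure.** Section 8.1.2 says 20 per group gives at least 80% power for a 1 SD difference. A two-sample t-test gives 87%, so the figure reproduces. No figure is given for contrast 3.

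**Step 1. Drift with no treatment effect** (baseline SD = 1)

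- Baseline gap between classes: 2ρ√(2/π) = 1.596ρ.
- Gap in start-to-end change: 1.596ρ(1 − r), in favour of the predicted non-responders.
- SD of change within a class: √[2(1 − r) − (2/π)ρ²(1 − r)²].
- Spurious d = gap ÷ SD. The t-test has noncentrality d√(30/2).

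| r | ρ | Gap in change | SD of change | d | False-positive rate |
|---|---|---|---|---|---|
| 0.5 | 0.4 | 0.319 | 0.987 | 0.32 | 23% |
| 0.5 | 0.7 | 0.559 | 0.960 | 0.58 | 60% |
| 0.7 | 0.4 | 0.191 | 0.769 | 0.25 | 16% |
| 0.7 | 0.7 | 0.335 | 0.756 | 0.44 | 39% |
| 0.85 | 0.4 | 0.096 | 0.546 | 0.18 | 10% |
| 0.85 | 0.7 | 0.168 | 0.541 | 0.31 | 22% |

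A simulation of 4,000 trials per setting agreed within about 2 percentage points. At ρ = 0 the rate was 5%, so this mechanism adds nothing in a region unrelated to the classifier.

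**Step 2. Direction.** In the same simulation, a significant increase within the drug cell occurred in 7% to 35% of trials, against 2.5% by chance. Within the placebo cell it occurred in about 1% or fewer.

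**Step 3. What item 4 does.** Write P for placebo, D for drug, N for no treatment, with subscripts R and NR for class.

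- One pooled untreated mean: (P_R − N) − (D_NR − N) = P_R − D_NR. It cancels, and the rates above are unchanged.
- Class-matched: (P_R − N_R) − (D_NR − N_NR). The drift cancels, and the simulated error rate was about 5%.

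The class-matched version still equals [placebo effect in NR − drug effect in NR] + [placebo effect in R − placebo effect in NR]. The second bracket is a class difference. The plan expects it not to be zero for pain, since section 8.1.2 takes the response of non-responders as negligible.

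**Step 4. Comparisons randomised within class.** Drug versus placebo within predicted non-responders had a simulated error rate of 5% in every setting. Power, in SDs of the analysed measure:

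- Drug versus placebo within a class, 30 versus 30: 97% for 1 SD, 48% for 0.5 SD.
- Arm by class, same two arms in both classes: SE = √(4/30) = 0.365; about 78% for a 1 SD difference between the two effects.
- Placebo versus no treatment within a class, 30 versus 10: SE = √(1/30 + 1/10) = 0.365; about 76% for 1 SD.
- Off-diagonal contrast with class-matched subtraction: SE = √(2/30 + 2/10) = 0.516; about 49% for 1 SD.

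**The case against.** **The two cells were chosen for a reason.** Under the study's hypothesis, placebo in predicted responders shows placebo analgesia, and drug in predicted non-responders shows drug analgesia with little placebo response. That justifies describing each cell. It does not make the difference between them a treatment effect.

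**Item 4 may already be class-matched.** Untreated participants are randomised within class, and section 2.1.1 gives them the task of controlling regression to the mean. A reader might infer that the plan subtracts one pooled untreated mean; section 8.1.1 does not say so. It does not say class-matched either, and it does not define the confound. This answers the false-positive rate if the matching is written in, but not the confounding in step 3.

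**Change scores protect.** They remove stable class differences, and this stands. They do not remove regression to the mean or a class-by-time difference.

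**The test may differ from the one computed.** Looking for distinct increases could mean finding an increase in each cell and then comparing the maps. Step 2 covers that reading: a false drug-cell increase remains. A reader might infer that the drift would create two spurious circuits. It would not, because it pushes the placebo cell down.

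**These are post-hoc contrasts, and the endpoint in section 2.3.1 is pain.** True, but section 1.2 calls the primary outcomes brain parameters, and the hypothesis under 2.1.1 is about circuitry.

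**Conclusion.** The concern holds for contrast 3. As written, it ties a randomised treatment to a non-randomised class and cannot support a conclusion about placebo versus drug circuitry.

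On the connectivity measure used for classification, an uncorrected 5% test would be positive in about 10% to 60% of trials with no treatment effect. That range rests on the assumed r and ρ, even dropout and 30 completers per cell. It is not a rate for the whole brain: it applies before multiple-comparison correction, and regions unrelated to the classifier are little affected.

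A reader might extend the criticism to contrast 2, which uses the same cells. Nothing here supports that: contrast 2 looks for decreases common to both cells, and opposite drifts work against finding them. Contrast 1 is within class and is not in question.

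**What to change.** Amend section 8.1.1 before unblinding:

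1. For contrast 3, estimate drug versus placebo within each predicted class, including predicted responders, for whom no such comparison is listed.
2. Test the arm-by-class term with the same two arms in both classes, using the Visit 5 scan adjusted for the Visit 2 scan.
3. Estimate the placebo effect as placebo versus no treatment within class.
4. State that the item 4 correction is class-matched, and name the confound that it addresses.
5. Define how a distinct increase is tested.
6. State that the direct comparison of the two off-diagonal cells is descriptive and will not be read as placebo versus drug circuitry.

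Two shortcuts do not suffice. Adjusting the off-diagonal comparison for the baseline scan brought simulated error back to about 5% or below, but treatment stays tied to class. Comparing drug versus placebo in non-responders with placebo versus no treatment in responders has the same fault and is not an arm-by-class term. Its SE is √(2/30 + 1/30 + 1/10) = 0.447, which gives about 61% power for a 1 SD difference between the two effects.

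The cost is analysis wording, because the stratified randomisation already exists. The price in precision is about 76% power for 1 SD where the untreated arm is the comparator (30 versus 10), and about 78% for the arm-by-class term.

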8.1.2 Sample Size and Accrual

Statistical power can be estimated based on the Cohen's d effect sizes for differences in pain with 6 weeks of treatment. For responders, based on our preliminary results, we anticipate a mean decrease of 2.5 units on a 0-10 scales with an estimated SD of 3, which results in an effect size estimate of 0.83. In non-responders, the mean decrease in pain is negligible and we do not expect to have enough power to detect this.

Power analyses in G*Power 3.1.3 indicated that we will have ample power to detect pre-to-post changes within a group; with an estimated effect size of $d = 0.8$, power would exceed 95% with a sample of 23 participants. In terms of a between-group comparison, assuming an effect size estimate of $d = 0.8$ across groups, power would exceed 95% for a sample size of $n = 42$ per group. Thus, the total sample size of 210 would provide for adequate power, even accounting for

potential dropout and/or lower-than-expected effect sizes. Assuming that we recruited 70 participants per group, for example, would mean that we could detect between-group effects as small as $d = 0.5$ with power exceeding 80%.

Power analysis for gender: The preliminary gender analyses from phase 1 subjects provide the means to calculate the power necessary for detecting gender effects in placebo propensity. The original sample sizes from phase 1 were based on treating gender and age as covariates of no interest. Based on an anticipated medium-sized effect using Cohen's conventions (Cohen, 1992), calculations in `chi2power` in Stata indicated that for $n=82$ and for $\alpha = 0.05$ we obtain power = 0.31. Instead if we double the number of subjects then we reach adequate detection power: assuming that males have 30% while females 50% placebo incidence rate, for $\alpha = 0.05$ and $n=160$ we obtain just adequate power = 0.74. Therefore all data from phase 1 and 2 will be combined to assess effect of gender on placebo response.

Our previous fMRI results show that 20 per group should be adequate given the preliminary results and earlier studies. Also, 20 per group allows for 80+% statistical power for effect sizes of 1 SD difference between groups. For DTI and T1 studies our earlier studies indicate that 20/group for within-subject contrasts is adequate but may be just at the limit for whole-brain contrasts for detecting between-group differences. We can overcome this obstacle by using targeted analyses of relevant brain areas. For example, simply removing the cerebellum and occipital cortex voxels from such analyses results in improving on multiple comparison cost by a factor of 2.

The results from Phase 1 affirm the above power calculations. Moreover they indicate that increasing the n for each of the treatment groups by 50% (as proposed in the gender supplement application) can lead to identifying effects that currently remain either non-significant or borderline significant.

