2.3 Endpoints

- 2.3.1 Endpoint for primary objective: (1) Placebo response (defined as > 20% reduction in pain intensity following placebo treatment, or defined from pain app ratings using permutation with 0.05 p-value cut-off) versus active treatment response (reduction in pain intensity following naproxen/omeprazole treatment)
- 2.3.2 Endpoints for secondary objective: (1) Testing the specificity and sensitivity of the brain and behavioral parameters from Phase 1, in combination with the TOPPP developed from the study interviews, as predictive markers for response in Phase 2. These parameters will be considered validated if together are at least 80% accurate in stratifying responders from non-responders.
- 2.3.3 Endpoint for gender objective: (1) Testing for females showing higher incidence of placebo response using combined outcomes from phase 1 and phase 2 data.

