(2) The blinded assessor will be responsible for initiating the preprocessing of the brain images and extracting the connectivity values between frontal and sensorimotor regions ("sign permutation value"). This extraction will be done within 4 days after the MRI was collected, which provides enough time to calculate this connectivity and the likelihood of response (see below), as well as adequate time to give the result to the pharmacy (see below).

(3) After obtaining the connectivity values, the blinded assessor will enter these along with the 2 questionnaire subscores into the model on page 10 to determine subject group identification. The model generates a response likelihood from 0 to 1, and those individuals with a p-value \geq 0.5 will be labeled as responders; all others will be labeled as non-responders.

(4) After response group identification, the blinded assessor will then send an email with subject ID, classification group, and randomization code to the Northwestern University Research Pharmacy email [contact]. The research pharmacy will have two independent randomization sequences for responders (Group A) and non-responders (Group B). Each group independently will be allocated in a 3:3:1 ratio (active treatment, placebo treatment, and no treatment, respectively) by the research pharmacy. Therefore, the pharmacist will be unblinded to identification and treatment allocation.

The unblinded monitor who is responsible for phone app compliance will be partially unblinded, remaining blinded to active vs placebo assignments but unblinded with respect to treatment vs no treatment groups, as the pain rating app will query participants "Have you taken today's medication?" The remaining staff members will be completely blinded to both treatment vs no-treatment allocation and within the treatment allocation to active vs placebo treatments

A one-week interim period was chosen to allow enough time for selected study staff to run the prediction analysis and send this information to the pharmacy, as well provide another week of additional baseline pain app ratings. The duration of this period might be slightly longer or shorter depending upon how quickly the model is run, but it will be within the visit window specified in this protocol, which is \pm 5 days

- Visit 3 (week 0): Start of Treatment Period (30-45 min).

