We examine the differences in change in pain for placebo responders versus non-responders and the interaction between active treatment and response type. We can estimate statistical power based on the Cohen's *d* effect sizes for differences in pain with 6-week placebo treatment. For responders, based on our preliminary results, we anticipate a mean decrease of 3 units on a 0-10 scales with an estimated SD of 15, which results in an effect size estimate of 2.0. In non-responders the mean decrease in pain is negligible and we do not expect to have enough power to detect this. Power analyses in G*Power 3.1.3 indicated that we will have ample power. Even with a conservative estimated effect size of $d = 1.0$, power would be 80% for a sample size of $n = 17$ per group which would allow to also detect the interaction effects. In addition, it ensures adequate sample sizes even assuming some attrition in each group. For brain imaging contrasts, fMRI results show that 20 per group should be adequate given the preliminary results and earlier studies. For DTI and T1 studies our earlier studies indicate that 25/group for within subject contrasts is adequate but may be just at the limit for whole-brain contrasts for detecting between-group differences.

Phase 1 results are consistent with above power calculations. They also show that a number of predictors were only borderline significant. Thus, increasing the number of treatment arm subjects by an additional 40 patients would provide opportunity to detect smaller effects and to test for gender dependence of placebo response.

J) Stopping Rules

This study will be stopped prior to its completion if: (1) the intervention is associated with adverse effects that call into question the safety of the intervention; (2) difficulty in study recruitment or retention will significantly impact the ability to evaluate the study endpoints; (3) any new information becomes available during the trial that necessitates stopping the trial; or (4) other situations occur that might warrant stopping the trial.

K) Designation of an Independent Monitor

The Independent Monitor for this study is [name] [name]. [name] is not associated with this research project and thus works independently of the PI, [name]. Since [name] is leaving, we need a new person to do this for us.

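### Section 8.1.2's between-group power of more than 95% ignores misclassification by Equation 1 and the actual placebo-arm cell sizes; at the Phase 1 accuracy of 94% it is about 92% (45 per class) or 78% (30 completers)

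*Combined protocol and SAP*

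**What the plan says.** Section 8.1.2 gives one effect. In responders: "For responders, based on our preliminary results, we anticipate a mean decrease of 2.5 units on a 0-10 scales". The SD is put at 3, so the standardised effect is 2.5/3 = 0.83. On the other side: "In non-responders, the mean decrease in pain is negligible". The power claim follows: "assuming an effect size estimate of $d = 0.8$ across groups, power would exceed 95"%, at 42 per group. The groups are not named. The section adds that 210 in total leaves room for dropout or smaller effects, and illustrates this with 70 per group and d = 0.5.

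DSMP 4.I (Justification of Sample Size) does name a contrast: "We examine the differences in change in pain for placebo responders versus non-responders and the interaction between active treatment and response type". Its inputs differ: a fall of 3, a printed SD of 15 and an effect size of 2.0.

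Section 6.0 defines a responder by the observed change in pain (a fall of at least 20%, or a permutation test). Phase 2 groups are formed differently. Equation 1 (section 2.1.4) is applied before treatment, and under section 5.2.1 "those individuals with a p-value \geq 0.5 will be labeled as responders; all others will be labeled as non-responders". Randomisation is 3:3:1 within each predicted class, and objective 2.1.1 is framed on patients so classified. Section 1.3 reports 94% accuracy for the final Phase 1 model. Section 2.3.2 sets the bar for the new cohort: "These parameters will be considered validated if together are at least 80% accurate in stratifying responders from non-responders".

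**The concern.** The effect size describes patients who do respond against patients who do not. The groups that Phase 2 compares are predicted responders and predicted non-responders. Any classification error puts some non-responders in the first group and some responders in the second, which pulls the two means together. The plan expects some error and would accept more, but no section carries that error into the power calculation. The 42 per group in the power statement is also more than the roughly 30 per class expected to complete in the placebo arm.

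What is at stake is how a null result is read. If the predicted classes show no clear difference in pain under placebo, a documented power above 95% invites the conclusion that they do not differ, although the real chance of missing a difference was larger than stated.

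**Working it through.** **Inputs from the documents**
- Fall of 2.5 in responders, SD 3, negligible fall in non-responders (8.1.2). Negligible is taken as 0.
- About 50% responders (8.1.1).
- Accuracy 94% in Phase 1 (1.3); validation floor 80% (2.3.2).
- Placebo arm: 45 per predicted class randomised; attrition about 33%, 210 to 140 (5.3). If attrition is even, 45 x 140/210 = 30 per class complete.

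**Assumptions added here**
- Two-sided alpha 0.05. Section 8.1.2 states an alpha only for the gender calculation.
- Sensitivity equal to specificity.
- SD 3 within each true class.
- Errors unrelated to the size of the fall within each true class.

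**Step 1: reproduce the plan.** A two-sample t-test (noncentral t) with d = 0.8 and 42 per group gives 95.2%. The n for 95% is 41.6, which rounds up to 42. A one-sided test would need only 35 per group, so two-sided 0.05 is the match. The 70-per-group, d = 0.5 example gives 83.6%, as claimed. The plan's arithmetic is sound for the inputs it uses.

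**Step 2: dilution.** The mean fall is 2.5 x PPV in predicted responders and 2.5 x (1 - NPV) in predicted non-responders, so the difference is 2.5 x (PPV + NPV - 1). With 50% responders and accuracy a on both sides, PPV = NPV = a. Then:
- difference = 2.5 x (2a - 1)
- within-class SD = sqrt(9 + 6.25 x a x (1 - a))

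For a = 0.94: 2.5 x 0.88 = 2.2; SD = sqrt(9.3525) = 3.06; d = 0.72.

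For a = 0.80: 2.5 x 0.60 = 1.5; SD = sqrt(10) = 3.16; d = 0.47.

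**Step 3: power**

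| Accuracy | Difference | SD | d | n = 45 | n = 42 | n = 30 |
|---|---|---|---|---|---|---|
| 100% | 2.5 | 3.00 | 0.83 | 97% | 97% | 89% |
| 94% | 2.2 | 3.06 | 0.72 | 92% | 90% | 78% |
| 90% | 2.0 | 3.09 | 0.65 | 86% | 83% | 69% |
| 80% | 1.5 | 3.16 | 0.47 | 60% | 57% | 44% |

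Simulating the mixture at 80% accuracy (40,000 trials per n) gives 60.4%, 57.2% and 43.7%. Power of 95% would need 52 per class at 94% accuracy and 117 at 80%.

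**Step 4: vary the assumptions, keeping 8.1.2's fall and SD**
- No SD inflation: 93% / 80% (n = 45 / 30) at 94% accuracy; 65% / 48% at 80%.
- Sensitivity and specificity of 0.9 and 0.7, or the reverse: d = 0.50, power 64% / 47%.
- Prevalence 40% or 60% at 80% accuracy: d = 0.46.

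**Step 5: vary the SD.** In DSMP 4.I the printed figures do not agree: 3/15 = 0.2, whereas an effect size of 2.0 with a fall of 3 implies SD 3/2.0 = 1.5. With a fall of 3 and SD 1.5, 80% accuracy gives a difference of 1.8, SD sqrt(2.25 + 9 x 0.16) = 1.92, d = 0.94 and power of 99% / 95% (n = 45 / 30). The conclusion therefore depends on which SD is right.

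**The case against.** Several points on the other side have force.

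- **The comparison is inferred.** Section 8.1.2 says only "In terms of a between-group comparison, assuming an effect size estimate of $d = 0.8$ across groups", and 70 per group is 210/3, which could mean three arms. This stands as a limit. The responder versus non-responder pair is still the only one given both means, and the DSMP names it.
- **80% is a floor.** This stands. A reader might infer from the bottom row of the table that the contrast is close to a coin flip. The documents do not support that as the expectation, because the accuracy they report is 94%.
- **The SD is disputed within the documents.** This stands (step 5). The figures here hold on 8.1.2's inputs only.
- **Two definitions of responder are mixed.** With falls distributed as N(2.5, 3) and N(0, 3) and a baseline of 5, a 20% fall is 1 unit. About 31% of true responders would miss it and about 37% of non-responders would reach it, so even perfect knowledge of the class would match that rule only about 66% of the time. The 80% bar therefore does not map cleanly onto the classes modelled here. The shrinkage factor PPV + NPV - 1 does not need normal outcomes, but it does need errors unrelated to the size of the fall. If errors cluster near the cut-off, the loss is smaller.
- **The plan already allows for smaller effects.** The 70-per-group example would give 79.6% at d = 0.47, but no predicted-class cell within an arm reaches 70.
- **The written pain model is different.** Section 4.4 sets out a mixed model on daily ratings with the three predictors as separate terms, so these figures are not that model's power. They are on the same footing as 8.1.2, which is itself a t-test calculation.

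**Conclusion.** The point holds in a limited form. For the predicted-class contrast under placebo, on 8.1.2's own fall and SD, power above 95% is not what the design delivers. At the Phase 1 accuracy it is about 92% if all 45 per class are analysed and 78% with 30 completers. Even perfect classification gives 89% at 30. At the 80% floor it is 60% / 44%, as a lower-bound sensitivity case.

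This rests on 50% responders, no change in non-responders, equal sensitivity and specificity, errors unrelated to the size of the fall, two-sided alpha 0.05 and even attrition. It also rests on SD 3 rather than the 1.5 implied by the DSMP's effect size.

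Three stronger readings are not supported:
- The plan's calculation is not wrong for its inputs; n = 42 reproduces.
- The 80% figures are not the trial's expected power.
- They do not weaken the accuracy endpoint in 2.3.2, which is judged on sensitivity, specificity and accuracy, not on a comparison of class means.

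**What to change.** In 8.1.2:
1. Name the between-group comparison to which the power statement applies.
2. Reconcile the effect size and SD with DSMP 4.I, and correct whichever figures are wrong.
3. For the predicted-class contrast, replace the more-than-95% claim with power at the actual cell sizes (45 randomised, about 30 completing). Use 94% accuracy as the planning case and 80% as the lower-bound sensitivity case, and list the assumptions. If 8.1.2's inputs are kept, the figures are 92% / 78% and 60% / 44%. If the SD changes, recompute them.
4. Stop citing the 70-per-group example in support of this contrast.

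Make DSMP 4.I consistent with the result. The change is to wording only, and enrolment stays as it is. The cost is a less favourable stated power.
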